#### *4.4.2 Main secondary efficacy analyses*

The main secondary efficacy analyses will include comparison the intervention group and the control group for the 12-week endpoint analysis and three study groups after the re-randomization at 12 weeks, including the continue training group, stop training group and the control group at the baseline randomization, for the 24 weeks endpoint analysis. All statistical tests of the secondary analyses will be 2-sided, both 95% confidence intervals and p values will be reported.

- 1) The mean value of changes in scores of global cognitive functions from baseline to 12 weeks will be compared using independent t-test between the intervention group and control group. In cases any of domains' score not following normal distribution, if the transformation is not feasible, either the Wilcoxon test or Friedman M test will be used.
- 2) Difference in the proportion of improvement in global cognitive function after 24 weeks will be compared using Pearson chi-square test between continue training group and control group. Adjustment will be performed if necessary.

- 3) The mean value of changes in scores of global cognitive functions from baseline to 24 weeks will be compared using independent t-test between continue training group and control group. Adjustment will be performed if necessary.
  
- 4) The mean value of changes in scores of global cognitive functions from baseline to 24 weeks will be compared using independent t-test between the stop training group and control group. Adjustment will be performed if necessary.

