## ***2.5 Outcomes***

### ***2.5.1 Primary outcome***

The primary endpoint of the study will be the proportion of subjects with improved global cognitive function at 12 weeks. As described in section 2.3, the cognitive function will be evaluated by BCAT. The BCAT will include four distinct brain functions, namely processing speed, working memory, episodic memory and visuospatial. The global cognitive function score will be calculated as the average of scores across each cognitive domain. In the DELIGHT trial, clinically significant improvement in cognitive function was defined as a Z-value of the overall BCAT score that was 0.67 SD (2 points of task score) higher than the baseline Z-value after 12 weeks training. The Z-value for each cognitive domain can be obtained by referring to the Z score conversion table (Table.1.2).

Table 1. The correspondence between BCAT cognitive ability scores and Z-scores

BCAT score	Z-score
19	3.00 (2.83 ~ 3.17)
18	2.67 (2.50 ~ 2.83)
17	2.33 (2.17 ~ 2.50)
16	2.00 (1.83 ~ 2.17)
15	1.67 (1.50 ~ 1.83)
14	1.33 (1.17 ~ 1.50)
13	1.00 (0.83 ~ 1.17)
12	0.67 (0.50 ~ 0.83)
11	0.33 (0.17 ~ 0.50)
10	0.00 (-0.17 ~ 0.17)
9	-0.33 (-0.50 ~ -0.17)
8	-0.67 (-0.83 ~ -0.5)
7	-1.00 (-1.17 ~ -0.83)
6	-1.33 (-1.50 ~ -1.17)
5	-1.67 (-1.83 ~ -1.50)
4	-2.00 (-2.17 ~ -1.83)
3	-2.33 (-2.50 ~ -2.17)
2	-2.67 (-2.83 ~ -2.50)
1	-3.00 (-3.17 ~ -2.83)

Table 2. Threshold for basic cognitive impairment in different age groups based on BCAT

	18-29 years old	30-39 years old	40-49 years old	50-59 years old	60-59 years old	Over 70 years old
processing speed	-0.16	-0.43	-0.69	-1.09	-1.39	-1.71
working memory	-0.25	-0.45	-0.74	-1.01	-1.26	-1.43
episodic memory	-0.34	-0.52	-0.80	-1.07	-1.20	-1.47
visual space	-0.53	-0.69	-0.76	-0.90	-1.05	-1.22

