#### ***4.9 Trial progress and actual sample size description***

COG-T-CHD completed enrollment of all patients on November 17, 2023, with a total of 224 patients enrolled. We also updated the research progress information on ClinicalTrials. The actual sample size is larger than the calculated sample size, which is specifically explained here. During the initial implementation of the scheme, there were 32 subjects whose MRI data were not collected in the baseline period, which belonged to the scheme deviation. In order to ensure the integrity of the exploratory outcome indicators, 24 subjects were added to the original sample size during the inclusion process. The confidence in the original sample size was calculated using the primary outcome measure, so the primary endpoint was not missing and was not affected in any way. This study was a randomized double-blind trial, and all subjects were not blinded in the study, so the randomness of the scheme was not affected.

Reference:

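### SAP 4.4.2 item 1 allows a Friedman test between two independent arms and ties its fallback to domain scores; ANCOVA would make items 1, 3 and 4 more precise at no data cost

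*SAP*

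**What the plan says.** Item 1 of Section 4.4.2 concerns the intervention and control arms at week 12: "The mean value of changes in scores of global cognitive functions from baseline to 12 weeks will be compared using independent t-test". Its fallback has two conditions, "In cases any of domains' score not following normal distribution" and "if the transformation is not feasible". If both hold, "either the Wilcoxon test or Friedman M test will be used". No rule chooses between the two tests, and the type of Wilcoxon test is not named.

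Section 4.1 gives the general rule: Shapiro-Wilk, then a transformation, then a Wilcoxon test. It does not mention Friedman. Section 2.5.1 defines the analysed score: "The global cognitive function score will be calculated as the average of scores across each cognitive domain". There are four domains.

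Items 2 to 4 are the 24-week comparisons with control. Item 2 is binary: "Difference in the proportion of improvement in global cognitive function after 24 weeks will be compared using Pearson chi-square test". Items 3 and 4 are t-tests on the change in global score for the continue-training and stop-training groups. Each of the three ends "Adjustment will be performed if necessary". Item 1 has no such sentence.

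**The concern.** One of the two named fallback tests does not fit the design. Each patient contributes one change score to item 1, and patients in different arms are not matched, so there are no blocks within which Friedman's test could rank.

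The condition for leaving the t-test also looks at the wrong variable. A domain score can fail a normality test while the change in the average of four domains is close to normal. The planned mean difference would then give way to a rank comparison for no good reason.

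A separate matter is precision. The trial collects the baseline global score and randomises within age and education strata, but the change-score t-tests use the baseline only by subtraction. This matters most at week 24, where the intervention arm has been split in two. Finally, the adjustment sentence leaves open what is adjusted and when, so the choice could be made after the 24-week data are seen.

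**Working it through.** **Figures in the plan.** Section 4.4.2 states no sample size or power of its own. The only calculation is for the primary outcome (Section 2.3: 30% vs 10%, two-sided 5%, 90% power). It reproduces with the unpooled formula: (1.960 + 1.282)² × (0.21 + 0.09) / 0.04 = 78.8, so 79 per arm; 79 / 0.8 = 98.75, so 99 per arm and 198 in all. It is not in dispute here.

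**Group sizes.** Section 4.9 reports enrolment "with a total of 224 patients enrolled". 224 / 2 = 112 per arm, and with the 20% loss of Section 2.3, 112 × 0.8 = 89.6, about 90. Section 2.1 re-randomises the intervention arm 1:1 at week 12, giving 45 vs 90 controls at week 24 if no more are lost.

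**Friedman.** No arithmetic applies. Item 1 has two independent groups and one value per patient; Friedman needs several related values per block.

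**Trigger, first condition only.** Four independent normal scores each tested at 5% give 1 − 0.95⁴ = 18.5% with at least one failure. Simulated Shapiro-Wilk tests (3,000 data sets, 180 patients, continuous normal scores, domain correlation 0 to 0.7) gave 17-19% for any of four, against 4.8-5.3% for the global change.

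**Cost of a needless switch.** Simulated power on normal data (8,000 trials each), t-test to Wilcoxon:
- 90 vs 90: 0.796 to 0.777, 0.803 to 0.782 and 0.798 to 0.780 for r = 0.5, 0.7 and 0.9
- 45 vs 90: 0.790 to 0.776, 0.798 to 0.780 and 0.796 to 0.771

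**Precision.** Let r be the correlation between baseline and follow-up global score, with equal variances σ². The SAP gives no r, so 0.5, 0.7 and 0.9 are assumed.
- Change score: variance 2σ²(1 − r)
- ANCOVA: variance σ²(1 − r²)
- Ratio: (1 + r)/2
- Power where the t-test has 80%: Φ(2.802/√ratio − 1.960)
- Difference detectable with 80% power, in SD of the score: 2.802 × √[V(1/n₁ + 1/n₀)], where V is the variance above with σ = 1

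| r | Ratio | 80% power becomes | Detectable, 90 vs 90 (t-test, ANCOVA) | Detectable, 45 vs 90 (t-test, ANCOVA) |
|---|---|---|---|---|
| 0.5 | 0.75 | 90% | 0.42, 0.36 | 0.51, 0.44 |
| 0.7 | 0.85 | 86% | 0.32, 0.30 | 0.40, 0.37 |
| 0.9 | 0.95 | 82% | 0.187, 0.182 | 0.229, 0.223 |

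Simulated ANCOVA power with baseline and both strata agreed: 0.890, 0.851 and 0.813 at 90 vs 90; 0.892, 0.852 and 0.804 at 45 vs 90. Type I error was 0.045-0.052 for the t-test, ANCOVA and Wilcoxon.

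**Multiplicity.** Items 3 and 4 share one control group, so their statistics have correlation (1/90)/(1/45 + 1/90) = 1/3. With each tested at 5%, the chance of at least one false positive is 9.5%. For items 2 to 4 together a simulation (20,000 trials, r = 0.7) gave about 12%.

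**The case against.** Several objections have force.

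- **ANCOVA corrects no error.** This stands. The change-score t-test is valid under randomisation and is fully named. The gain depends on an r that the SAP does not give and on equal variances, and at r = 0.9 it is negligible. The 80% power used as a yardstick is not in the SAP, which powers only the primary outcome. ANCOVA is still worth having because it uses data already collected and costs almost nothing.
- **Section 4.1 already supplies a workable fallback.** This also stands: the Friedman option is a local slip, at odds with 4.1, rather than a gap with no way out. It also means that 4.1 must be amended together with 4.4.2, or the two would conflict.
- **The trigger sentence is loosely worded.** It may mean only that whichever score is non-normal gets a non-parametric test. The literal reading is plausible but not certain.
- **The adjustment sentence occurs only in the 24-week, three-group items.** That suggests multiplicity, though it does not prove it. The SAP claims no family-wise control for secondary analyses, so the 9.5% breaks no promise.

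A reader might go further and infer that the t-test will almost always be abandoned. If domain scores are whole points, as the listing in Table 1 of Section 2.5.1 might suggest, at least one of four fails Shapiro-Wilk in 98-100% of simulated data sets of 180. That result rests on an assumed whole-point scale with SD 2-3 and mean 7-10, and it covers only the first condition. The SAP also requires that no transformation be feasible, so no switch rate follows from the documents.

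**Conclusion.** The point holds, for secondary analyses only. The Friedman option is wrong as written: it cannot compare two independent arms, and it disagrees with Section 4.1. The domain trigger, read literally, tests the wrong variable and is met in 17-19% of data sets with normal domain scores, against 5% for the global change. Its practical cost is small: about 2 points of power, and a rank comparison in place of a mean difference.

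ANCOVA is an improvement in precision, with variance 25%, 15% or 5% lower for assumed r of 0.5, 0.7 or 0.9 and equal variances. The undefined adjustment is a lesser matter of missing detail.

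A reader might infer that the planned t-tests are invalid or that the primary result is at risk. Neither follows: the t-tests keep their type I error, and the primary chi-square test in Section 4.4.1 is untouched.

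**What to change.** - **Item 1:** delete the Friedman option and the domain-score trigger.
- **Items 1, 3 and 4:** analyse the week-12 or week-24 global BCAT score by ANCOVA on arm, baseline global BCAT, age stratum (≥75, <75) and education stratum. Report the adjusted mean difference with its 95% CI. Modelling the change with baseline as covariate gives the same arm estimate, so the stated outcome is kept.
- **Sensitivity:** keep the Wilcoxon rank-sum (Mann-Whitney) test, named as such, as a fixed sensitivity analysis that no normality test triggers.
- **Section 4.1:** state that its Shapiro-Wilk, transformation and Wilcoxon sequence does not apply to these comparisons.
- **Items 2 to 4 (lesser point):** replace the adjustment sentence with a stated choice, either Holm over items 2 to 4 or a statement that the p values are descriptive. ANCOVA does not settle this. A stratified analysis of item 2 is optional and depends on stratum sizes, which the SAP does not give; at about 45 vs 90, sparse strata are possible.

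The cost is SAP wording and minor programming, with no new data. Enrolment is complete, and Section 2.1 unblinds subjects after the 12-week visit, so the amendment must be dated and shown to precede any analysis by arm. Section 4.2 starts analysis only after the 24-week visits.

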#### *4.4.3 Main exploratory efficacy analyses*

All participants in this trial collected multimodal Magnetic resonance imaging (MRI) data including the structural MRI, resting-state functional MRI, Diffusion tensor imaging (DTI) and Arterial spin labeling (ASL) perfusion data. First, the preprocessing software such as SPM and FSL were used to preprocess the imaging data including the realignment, segmentation and registration of the brain images. Then the structural and functional changes brought by training were compared between two groups of participants. Moreover, the deep learning approaches were used to identify the neural signatures of cognitive impairment before and after the cognitive training in patients with coronary heart disease. Combining the neuropsychological scales, demographic information and biological indices, we further aimed to establish a unified predictive model of cognitive impairment and recovery encompassing the neurobiological correlates as well as impact of multiple potential covariates.

#### **4.5 Subgroups**

The following subgroups will be analysis in both primary and secondary outcomes to test the consistency:

Gender: female, or male;

Age:  $\geq 70$  years old, or  $< 70$  years old at baseline visit;

Education: completion of junior high school and below, or senior high school and above

Anticoagulant usage: reporting using anticoagulant drugs in baseline assessment, or not

#### ***4.6 Sensitivity analysis***

The ITT analysis and per-protocol analysis will also be employed as sensitivity analysis for the primary outcome.

#### ***4.7 Safety analysis***

The occurrence of safety issues and serious adverse events during the implementation of this study is anticipated to be minimal. The participants will undergo regular monitoring for the following adverse events but no analysis is planned to perform.

##### **Adverse Events (AE)**

Adverse events (AE) are defined as undesirable symptoms, signs, diseases, or exacerbations of the above that occur during the study and may be related to the study. The determination of an adverse event should be based on a diagnostic or abnormal indicator. Events prior to randomization during the trial were not considered adverse events.

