#### ***4.3 Discontinuing/Intervention Deviation***

Given the intervention's nature, the study will not result in any foreseeable harm or an objective need to stop the intervention. The patient will be informed that he or she may request a suspension of training or withdrawal from the study at any time for any reason and

that this will not affect his or her routine medical treatment. If the withdraw occurs, the existing data will be retained and the subsequent data will be marked as missing data. This study defines missing follow-up as an uncertain primary outcome in randomized participants. If a participant fails to return to the clinic for a scheduled study visit, the site must make every effort to reconnect with the participants in certain window. In general, retrospective visits are not permitted. However, the adverse measure will still be recorded and involved.

There are no plans to modify the assigned intervention. If adverse events occur, investigators will determine whether continued intervention is harmful to the safety or health of the participants, or sponsor requires participants to permanently stop the intervention, then the patient's intervention will be discontinued.

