##### **Serious Adverse Events (SAE)**

In accordance with NHLBI and the OHRP Management Charter, a serious adverse event (SAE) is defined as meeting one of the following criteria:

- 1) resulting in fatality or posing a life-threatening risk;
- 2) causing severe and permanent disability;
- 3) requiring hospitalization or prolonged hospitalization;

- 4) leading to congenital abnormalities/birth defects in offspring;
- 5) being determined by investigator as a medical event that causes significant harm to the patient, necessitating medication or surgical intervention to prevent other conditions as outlined in the SAE (e.g., death, permanent disability, hospitalization).

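### The adverse event definition admits symptoms but then adds an undefined indicator test and a relatedness condition that the SAE list lacks, so symptom-only and judged-unrelated events may be under-counted

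*SAP*

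**What the plan says.** The Adverse Events subsection of SAP section 4.7 has three parts.

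- It defines AEs as "undesirable symptoms, signs, diseases, or exacerbations of the above that occur during the study and may be related to the study".
- It then sets a test: "The determination of an adverse event should be based on a diagnostic or abnormal indicator".
- It fixes the starting point: "Events prior to randomization during the trial were not considered adverse events".

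The Serious Adverse Events subsection lists five criteria, any one of which is enough. The third is "requiring hospitalization or prolonged hospitalization". None of the five mentions relation to the study or an indicator.

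On use of the data, section 4.7 says: "The participants will undergo regular monitoring for the following adverse events but no analysis is planned to perform". Section 4.3 expects that "the study will not result in any foreseeable harm or an objective need to stop the intervention". It also gives AEs a practical role, because their occurrence prompts the investigator to assess whether going on with the intervention is harmful. For participants who miss visits it adds: "However, the adverse measure will still be recorded and involved".

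Section 2.1 names eight centres, unblinding after the 12-week visit and follow-up to week 24.

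**The concern.** There are two separate defects.

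The first is an internal conflict. A symptom is an AE in its own right under the opening sentence, where it is listed apart from signs and diseases. A symptom with neither a diagnosis nor an abnormal finding can fail the next sentence. One centre may count it and another may not, and both could point to the SAP.

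The second is a restriction in the wrong place. When relatedness is part of the definition, an event judged unrelated is left out of the count. It is not counted and then attributed. A reader of the results cannot review a judgement that has removed the event from the data. After week 12 that judgement is made with knowledge of the arm.

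At stake is which events are monitored under section 4.7 and which prompt the investigator's assessment under section 4.3. Adding a table of AEs by arm would not cure this, because a table can show only what the definition let in.

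**Working it through.** The SAP gives no AE rate or count, so there is no figure to reproduce. The check is to apply each stated rule to the same kinds of event, all with onset after randomisation.

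| Event | Opening sentence (type, possibly related) | Indicator sentence | SAE list |
|---|---|---|---|
| A. Symptom only, thought possibly related, not serious | AE | Unclear: fails on a strict reading, may pass on a loose one | Not an SAE |
| B. Diagnosed condition, judged unrelated, not serious | Not an AE | Passes | Not an SAE |
| C. Hospitalisation with a diagnosis, judged unrelated | Not an AE | Passes | SAE |
| D. Hospitalisation with a diagnosis, thought possibly related | AE | Passes | SAE |

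**Row A** shows the contradiction. The two sentences give different answers unless indicator is read loosely enough to include the symptom itself, and the SAP does not say whether it may be.

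**Row B** shows the effect of the relatedness condition. The event meets the indicator test and is still excluded.

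**Row C** shows the mismatch. Taken literally, the SAE list makes the event serious and adverse while the AE definition says it is not adverse at all. The alternative is that an SAE must first be an AE. The relatedness condition then carries over into the SAE count, and row C leaves both counts. The SAP does not choose between these readings.

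**Timing.** Under section 2.1, subjects are unblinded after the 12-week visit, the control group stops its intervention, and the digital therapy group is re-randomised to stop or continue training until week 24. From then on, whoever judges relatedness can know the arm and whether the participant is still training. An event in someone no longer training could more readily be judged unrelated. The condition can therefore remove events unequally between groups in weeks 12 to 24. Before week 12, if the blind holds, the judgement should not depend on the arm.

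**The case against.** The case against has several parts, and much of it stands.

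- **Recording is not determination.** A reader might infer that symptoms go unrecorded. The text does not say so. The indicator sentence is phrased as a recommendation, concerns what is determined to be an AE and is silent on what is written down. Section 4.7 promises regular monitoring and section 4.3 promises continued recording. The supportable claim is possible under-counting.
- **The relatedness condition does not hide training harms.** A complaint that a site thinks the training caused meets the condition by definition, and the threshold is low. Only the indicator sentence could exclude such a complaint. The condition is a restriction and does not contradict anything within the AE paragraph. The SAP names no specific harms of screen training, so none can be said to be lost.
- **The safety record would not be near-empty.** Diagnosed conditions and abnormal findings thought possibly related pass even a strict reading. On a literal reading, the SAE list captures every death and hospitalisation.
- **On the literal reading, the SAE mismatch is a labelling problem.** Row C is still captured as an SAE. This holds only if SAEs need not first be AEs, which the SAP leaves open.
- **No AE analysis is planned.** This limits the effect on reported results. It does not remove the effect on monitoring or on the assessments in section 4.3.
- **The protocol may hold fuller collection rules.** It may, and it is not at hand. The point concerns a rule that the SAP itself states, which would then have to agree with the protocol.
- **Late repair can introduce bias.** Section 4.9 reports enrolment complete, so new wording cannot change what was elicited at past visits. Searching notes with the arm known could create the imbalance the change is meant to prevent. This is right, and it limits the remedy.

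**Conclusion.** The point holds as a defect of definition that should be corrected. The symptom and indicator sentences conflict on a plain reading. The relatedness condition removes judged-unrelated events from the AE count. The SAE list carries neither condition, and the SAP does not say how the two definitions relate.

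The direction is towards under-counting of symptom-only and judged-unrelated events, with possible variation between centres and, after week 12, between arms. The size cannot be given. It depends on how many complaints lack a diagnosis or abnormal finding, how strictly sites read indicator, and how often events are judged unrelated, and the SAP supplies none of these. Any figure would rest wholly on an assumed capture rate.

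The conclusion assumes that sites apply the SAP wording as it stands. If the protocol or case report form already collects all events with a separate relatedness field, the defect is confined to the SAP text and the counts drawn from it. The efficacy conclusions are not affected.

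**What to change.** In the Adverse Events subsection of section 4.7:

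1. Remove the indicator sentence as a condition for counting an event.
2. Count every undesirable symptom, sign, disease or exacerbation with onset after randomisation, whatever its judged relatedness.
3. Keep relatedness as a separately recorded attribute of each event.
4. State that every SAE is also an AE.

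Check the revised text against the protocol so that both give one definition.

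If events already noted are reclassified under the new wording, those doing it should be blind to arm and apply the same rule at all eight centres. Such a review recovers only what was written down, and the report should say so.

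The cost is a wording change, somewhat more data entry and a less favourable safety count. The blinded reclassification is extra work and is needed only if past events are to be brought under the new definition.
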